**Table 5: Schedule of Assessments for Subjects From Group B Who Cross Over to Open-Label Ruxolitinib**

	Section	Crossover Eligibility Visit	Crossover Treatment Phase						Notes
			W1-W3 After Crossover				W4-W52 q4w After Crossover	W56+ q12w After Crossover	
			Day -1	D1	D8 (± 2d)	D15 (± 7d)	D22 (± 2d)	D7 (± 3d)	
Contact IXRS	7.2	X					X	X	
Review inclusion and exclusion criteria	7.5.1	X							To determine eligibility for crossover.
Prior/concomitant medications	7.4	X		X	X	X	X	X	
Vital signs	7.5.4	X		X	X	X	X	X	Vital signs collected after 5 min rest in recumbent, semirecumbent, or sitting position.
Physical examination, body weight	7.5.3	X		X	X	X	X	X	Comprehensive examination at the crossover eligibility visit and EOT; targeted examination at all other visits.
ECOG status	7.7.1	X*			X		X	X	* Must be 0, 1, or 2 to start ruxolitinib.
█/liver palpation	7.6.3	X			X		X	X	Using flexible ruler provided for study.
12-lead ECG	7.5.5	X					X*		* Week 52
Laboratory tests	7.5.6	X		X	X	X	X	X	See Table 6 and Table 7.
Review AEs	7.5.2	X		X	X	X	X	X	
Transfusion history/status	7.4	X							
Open-label ruxolitinib dispensed	7.10.2	X*					X	X	* Open-label ruxolitinib may be dispensed at the crossover eligibility visit.
Record first day of open-label ruxolitinib dosing	7.10.1	X							
Drug accountability	7.10.3						X	X	

**Table 6: Schedule of Laboratory Assessments for Subjects From Group B Who Cross Over to Open-Label Ruxolitinib**

	Section	Crossover Eligibility Visit Day -1	Crossover Treatment Phase						Notes
			W1-W3 after Cross Over				W4-52 q4w After Crossover	W56 + q12w After Crossover	
			D1	D8 (± 2d)	D15 (± 2d)	D22 (± 2d)	D7 (± 3d)	D7 (± 3d)	
Local laboratory assessments									
Hematology	7.5.6	X		X	X	X	X	X	
Coagulation panel	7.5.6	X							
Serum chemistries	7.5.6	X		X	X	X	X		
Urine pregnancy test	7.5.6.1	X					X	X	Females of childbearing potential if required by local regulations. Test should be repeated if required by local regulations.
Central laboratory samples*									* The central laboratory is the sponsor or designee.
Lipid panel	7.5.6	X					X	X	
Urinalysis	7.5.6	X					X	X	

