#### **5.4.3.2. Discontinuation of Study Drug for Nonhematologic Toxicity**

Study drug (ruxolitinib, anagrelide, or matching placebos) MUST be permanently discontinued if any 1 of the following AEs fails to resolve to  $\leq$  Grade 2 within 8 weeks of study drug interruption or if a lower restart dose or administration schedule subsequent to any of the following nonhematologic toxicities is either not available or likely to be clinically ineffective:

- The occurrence of a Grade 4 laboratory or nonlaboratory abnormality attributable to study treatment (ruxolitinib, anagrelide, or matching placebo).
- The occurrence of a Grade 3 laboratory or nonlaboratory abnormality attributable to study treatments (ruxolitinib, anagrelide, or matching placebo) that remains at Grade 3 or worse for > 7 days duration and, for laboratory abnormalities, is deemed clinically significant in the judgment of the investigator.

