### **5.4.4. Dose Modifications for Subjects Receiving Open-Label Treatment**

The dose increase, decrease, and discontinuation rules described in Sections 5.4.1, 5.4.2, and 5.4.3 will be followed for subjects receiving open-label anagrelide or open-label ruxolitinib. Table 2 should be used to identify dose levels for the individual study medications.

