**Table 4: Schedule of Laboratory Assessments**

[figure not shown]
	Section	Screening Days -35 to -8	Baseline Days -7 to -1	Blinded Treatment (All Subjects)						Open-Label Treatment		EOT	Safety Follow-Up 30-37d After Last Dose	Notes
										Subjects Who Do Not Cross Over	Subjects Who Cross Over			
				W1-W3			W4- W52 q4w	W34-W50 q4w (lab only)		W56+ q12w	W56+ q12w			
				D1	D8 (±2d)	D15 (± 2d)	D22 (± 2d)	D7 (± 3d)	D7 (± 3d)	D7 (± 7d)	D7 (± 7d)			
Local laboratory assessments											See Table 6			
Hematology	7.5.6	X	X*	X*	X	X	X	X**	X**	X		X	X	* Should be taken as close as possible to Day 1 but may be drawn up to 3 days before first dose. Only 1 sample for baseline/Day 1 is required. ** Weeks 32-52 are evaluation period for primary endpoint: Should ALL be carefully monitored by sites.
Ferritin level	7.5.6		X											
Coagulation panel	7.5.6	X	X*	X*								X		* Should be taken as close as possible to Day 1 but may be drawn up to 3 days before first dose. Only 1 sample for baseline/Day 1 is required.
Serum chemistries	7.5.6	X	X*	X*	X	X	X	X		X		X	X	* Should be taken as close as possible to Day 1 but may be drawn up to 3 days before first dose. Only 1 sample for baseline/Day 1 is required.
Urine pregnancy test	7.5.6.1			X				X		X				Females of childbearing potential. Test should be repeated if required by local regulations. Not needed if FSH elevated or amenorrheic > 1 year.

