**Table 7: Laboratory Tests: Required Analytes**

Serum Chemistry	Hematology	Urinalysis With Microscopic Examination	Hepatitis Screening	Coagulation
Albumin Alkaline phosphatase ALT AST Bicarbonate Blood urea nitrogen Calcium Chloride Creatinine Ferritin Glucose Lactate dehydrogenase Phosphate Potassium Sodium Total bilirubin Direct bilirubin (if total bilirubin is elevated above ULN) Total protein Uric acid	Complete blood count, including reporting of % blasts: Hemoglobin Hematocrit Platelet count Red blood cell count WBC count	Color and appearance pH and specific gravity Bilirubin Glucose Ketones Leukocytes Nitrite Occult blood Protein Urobilinogen	Hepatitis B surface antigen Hepatitis B surface antigen antibody Hepatitis A, B core antibody HBV-DNA HCV antibody HCV-RNA	PT aPTT INR
	Differential count, including:	Lipid Panel		Pregnancy Testing
	Basophils Eosinophils Lymphocytes Monocytes Neutrophils  Absolute values must be provided for: WBC differential laboratory results: Lymphocytes Neutrophils	Total cholesterol Triglycerides Low density lipoprotein High density lipoprotein		Female subjects of childbearing potential only require a serum test at screening and EOT and a urine pregnancy test at each study visit when the test is requested. Pregnancy tests (serum or urine) should be repeated if required by local regulations. FSH

Note: Additional tests may be required, as agreed by investigator and sponsor, based on emerging safety data.

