## **6.5. End of Treatment**

If a decision is made that the subject will withdraw from study participation, then an EOT visit should be conducted within 7 days after the last dose of study treatment. If the EOT visit coincides with a regular study visit, then the EOT evaluations will supersede those of that scheduled visit, and the data should be entered in the EOT visit in the eCRF. The subject should be encouraged to return for the follow-up visit.

If a study withdrawal occurs, or if the subject fails to return for visits, then the investigator must determine the primary reason for a subject's premature withdrawal from the study and record this information in the eCRF.

The investigator must contact the IXRS system to register the subject's discontinuation.

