#### **7.5.6. Laboratory Assessments**

All hematology laboratory assessments, serum chemistries, and coagulation parameters will be analyzed by local laboratories. Serology, urinalysis, and lipid panel will be analyzed by a central laboratory. Samples for hematology, serum chemistry, serology, coagulation tests, pregnancy, and FSH tests and urinalysis will be prepared using standard procedures. A complete list of laboratory assessments is shown in [Table 4](#) and [Table 6](#). Refer to the Laboratory Manual for further details and specifications for sample handling, processing, and shipping. Additional laboratory assessments may be conducted at investigator's discretion to understand safety findings or to support dose modifications.

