**The following changes are from Administrative Change 2 (dated 29 AUG 2017):**

8. **Section 6, Study Assessments (Table 5, Schedule of Assessments for Subjects From Group B Who Cross Over to Open-Label Ruxolitinib)**

**Description of change:** Assessments were added for the visits beginning 56 weeks after crossover and continuing every 12 weeks.

**Rationale for changes:** Addition of missing assessments.

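### Table 6 schedules no serum chemistry after Week 52 of crossover ruxolitinib, while subjects who stay on open-label ruxolitinib keep it every 12 weeks

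*Protocol*

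**What the plan says.** Protocol Table 6 is the laboratory schedule for Group B subjects who cross over. Its chemistry row is "Serum chemistries 7.5.6 X X X X X". The five marks fall at the crossover eligibility visit, Days 8, 15 and 22, and the 4-weekly visits from crossover Week 4 to 52. The next column, for 12-weekly visits from crossover Week 56, is empty. Hematology, urine pregnancy test, lipid panel and urinalysis are all marked in that column.

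In Table 4, the row "Serum chemistries" is marked every 12 weeks from Week 56 for open-label subjects who do not cross over, and again at end of treatment (EOT) and safety follow-up. For crossover subjects, Table 4 refers to Table 6.

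Section 5.4.4 says that the dose increase, decrease and discontinuation rules "will be followed for subjects receiving open-label anagrelide or open-label ruxolitinib". Those rules include Section 5.4.3.2, which lists "The occurrence of a Grade 4 laboratory or nonlaboratory abnormality attributable to study treatment" and also covers persistent Grade 3 abnormalities. Table 7 places the relevant analytes in the chemistry panel: "Albumin Alkaline phosphatase ALT AST Bicarbonate Blood urea nitrogen Calcium Chloride Creatinine". Section 7.5.6 allows extra laboratory tests at the investigator's discretion, "to understand safety findings or to support dose modifications".

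**The concern.** After crossover Week 52, these subjects have no scheduled chemistry while on drug. Subjects taking the same drug in Group A, also seen every 12 weeks, do. An asymptomatic Grade 3 or 4 rise in ALT, AST or creatinine would be found on treatment only if someone ordered an extra test, and an asymptomatic rise may give no reason to order one. The stopping rule stays in force, but nothing scheduled would trigger it for these analytes.

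The next scheduled panel would be the one at EOT, if Table 4's EOT column also covers crossover subjects (Table 6 has no such column). Section 6.5 says "an EOT visit should be conducted within 7 days after the last dose of study treatment", which is too late to guide dosing.

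There is also a smaller reporting issue. SAP Table 3.3.8 shows worst-grade chemistry shifts across all ruxolitinib-treated subjects, so the two ruxolitinib groups would enter it with unequal opportunity for detection.

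**Working it through.** The plan states no figure on this point, so the check compares the tables and counts visits.

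**Step 1. Is the cell really blank?** Each Table 6 row has the same number of cells, so the marks can be assigned to columns.

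| Row | Eligibility | D8, D15, D22 | W4–52, 4-weekly | W56+, 12-weekly |
|---|---|---|---|---|
| Hematology | X | X | X | X |
| Serum chemistries | X | X | X | blank |
| Urine pregnancy test | X | – | X | X |
| Lipid panel | X | – | X | X |
| Urinalysis | X | – | X | X |
| Coagulation panel | X | – | – | – |

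Chemistry matches hematology in every column except the last. A reading error in the table is therefore unlikely.

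**Step 2. Does other text fill it?** Table 5 marks laboratory tests from crossover Week 56 but refers to Tables 6 and 7 for their content. Table 7 lists analytes, not visits. Table 4 sends crossover subjects to Table 6. Section 7.5.6 covers only additional, discretionary tests. None of these schedules the panel.

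**Step 3. Panels up to crossover Week 52.** Days 8, 15 and 22 give 3. Weeks 4 to 52 every 4 weeks give 52/4 = 13. Total post-dose panels: 3 + 13 = 16.

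**Step 4. Panels missed afterwards.** The unmarked visits are crossover Weeks 56, 68, 80, 92 and so on. The number missed is the number of these weeks not exceeding (study week at end of follow-up − study week at crossover). Section 4.1.1 puts the earliest crossover at Week 56. Section 4.5 ends the study when the last subject reaches Week 156. Section 4.4 gives average participation of 24 to 36 months, roughly Weeks 104 to 156.

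| Crossover at study week | Followed to study week | Weeks on crossover drug | Panels missed |
|---|---|---|---|
| 56 | 104 | 48 | 0 |
| 56 | 130 | 74 | 2 |
| 56 | 156 | 100 | 4 |
| 68 | 156 | 88 | 3 |
| 80 | 156 | 76 | 2 |
| 92 | 156 | 64 | 1 |
| after 100 | 156 | under 56 | 0 |

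For crossover at Week 56 and follow-up to Week 156, the stretch without scheduled on-treatment chemistry is 100 − 52 = 48 weeks. The open-label interval in Group A is 12 weeks.

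**Step 5. Effect on SAP Table 3.3.8, to Week 156.** Group A has 16 panels to Week 52 by the same count, plus Weeks 56, 68, 80, 92, 104, 116, 128, 140 and 152: 16 + 9 = 25. A Week 56 crossover subject has 16 now and would have 16 + 4 = 20 after the fix. The blank cell accounts for 4 of the 25 − 16 = 9 panel difference. The other 5 come from Group A's longer time on ruxolitinib. Over the first 100 weeks on drug, Group A has 16 + 4 = 20 panels, so the fix makes the two groups equal at equal exposure.

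**The case against.** The strongest case on the other side is that this is a small matter. The gap opens only after a year of ruxolitinib and 16 panels, in an open-label extension. Section 1.5.1 reports no chemistry pattern suggesting a new concern in long-term treatment of essential thrombocythemia. Many subjects would miss few panels or none. All of this stands, and it limits the expected yield.

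The stopping rule also cannot run on 12-weekly panels alone. It depends on attribution, on a Grade 3 abnormality lasting more than 7 days, and on resolution within 8 weeks of interruption, so Group A needs extra tests to apply it too. That is correct. What the scheduled panel adds is first detection, and without it nothing prompts the follow-up tests.

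Other safeguards remain. Section 7.5.6 allows discretionary tests, and a note to Table 7 lets the investigator and sponsor agree on more if safety data call for them. Urinalysis still reports bilirubin, urobilinogen and protein, and liver palpation and physical examination continue. The extra tests need a trigger, and the continuing assessments do not measure ALT, AST or creatinine.

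The blank might also be deliberate. Table 4's open-label column is shared with subjects staying on anagrelide, for whom Section 1.5.2 calls for liver tests during therapy. The Protocol does not give this as a reason, and it would not explain why Group A keeps chemistry. Nor is oversight proven. Appendix K, Administrative Change 2, says "Assessments were added for the visits beginning 56 weeks after crossover and continuing every 12 weeks", but under Table 5 only. That fits an overlooked cell without establishing one.

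Finally, the rates of raised ALT (27.2%) and AST (18.6%) in Section 1.2.3.2 come from myelofibrosis trials and carry no grade. They are not used here to size the risk.

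**Conclusion.** The concern holds. Table 6 leaves a gap in scheduled chemistry that no other text in the Protocol or SAP fills or explains. Its size is 0 to 4 panels per crossover subject for follow-up to Weeks 104 to 156, with at most 48 weeks unmonitored by schedule within that horizon.

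The count assumes that visits follow the tables and that follow-up ends by the subject's Week 156. Because the study closes when the last subject reaches Week 156, an earlier-enrolled subject still on drug could miss one more panel per further 12 weeks. Accrual time and the number of Group B subjects expected to cross over are not given, so no trial-wide total can be stated.

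The hematologic stopping rules, the randomized-phase chemistry shift table (SAP Table 3.3.7) and the primary analysis are unaffected. This is a cheap improvement that should be made: it gives subjects on the same drug the same monitoring.

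**What to change.** Add an X for serum chemistries in Table 6 in the 12-weekly column from crossover Week 56. An administrative change is enough.

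The cost is one local chemistry panel at each 12-weekly visit, where blood is already drawn for hematology: 0 to 4 panels per crossover subject for follow-up to Weeks 104 to 156. No SAP change is needed. SAP Table 3.3.8 remains descriptive, and the part of its imbalance that reflects Group A's longer exposure will remain.

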#### 3.1. Subject Inclusion Criteria

A subject who meets all of the following criteria may be included in the study:

1. Men and women, aged 18 or older.
2. Subjects diagnosed with ET according to revised WHO 2016 criteria ([Appendix A](#); [Arber et al 2016](#)).
3. Subjects who are resistant to or intolerant of HU ([Appendix B](#)), that is, fulfilling at least 1 of the following criteria:
  - a. Platelet count  $> 600 \times 10^9/L$  after 3 months of at least 2 g/day of HU (2.5 g/day in subjects with a body weight over 80 kg) OR at the subject's maximally tolerated dose if that dose is  $< 2$  g/day.
  - b. Platelet count  $> 400 \times 10^9/L$  and WBC count  $< 2.5 \times 10^9/L$  or hemoglobin (Hgb)  $< 10$  g/dl at any dose of HU.
  - c. Presence of leg ulcers or other unacceptable muco-cutaneous manifestations at any dose of HU.
  - d. HU-related fever.
4. Platelet count  $\geq 650 \times 10^9/L$  at screening.
5. WBC  $\geq 11.0 \times 10^9/L$  at screening.
6. ECOG performance status 0 to 2.
7. Known status of JAKV617F mutation.

8. Willingness to avoid pregnancy or fathering children based on the following criteria ([Appendix G](#)):
  - a. Woman of nonchildbearing potential (ie, surgically sterile with a hysterectomy and/or bilateral oophorectomy OR  $\geq 12$  months of amenorrhea and at least 50 years of age).
  - b. Woman of childbearing potential who has a negative serum pregnancy test at screening and negative urinary test before the first dose on Day 1 and who agrees to take appropriate precautions to avoid pregnancy (with at least 99% certainty) from screening through safety follow-up. Permitted methods that are at least 99% effective in preventing pregnancy should be communicated to the subject and their understanding confirmed.
  - c. Man who agrees to take appropriate precautions to avoid fathering children (with at least 99% certainty) from screening through safety follow-up. Permitted methods that are at least 99% effective in preventing pregnancy should be communicated to the subject and their understanding confirmed.

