### **6.3.1. Transition Period Before Open-Label Period**

Upon completion of the Week 52 study visit for each individual subject, a period of approximately 2 to 4 weeks will be used to perform eCRF entry and cleaning of clinical data up to and including the Week 52 visit. During this period, the subject should continue on blinded study treatment (unless interrupted for safety reasons). When the data cleaning process is complete (procedure to be detailed in the Study Manual), the sponsor will authorize the unblinding of the subject's treatment assignment via the IXRS system (see Section 5.1.2.1) and perform the following actions:

- Contact the IXRS for treatment management.
- Schedule subject to return to clinic to begin the open-label treatment period or EOT visit.
- Conduct an unscheduled visit if necessary to perform safety assessments for determining eligibility to begin open-label treatment.

This period will end when the subject either begins receiving open-label treatment or is withdrawn from the study. It may be necessary to delay initiating the open-label treatment

period treatment once reaching Week 52 of the blinded treatment in order for the subject to meet these eligibility criteria (see Section 3). A delay of up to 4 weeks is permitted for this purpose. Additional study visits will be scheduled for all subjects the first 4 weeks after open-label ruxolitinib is initiated to permit safety evaluations and dose modification. Afterward, the regular study schedule will be resumed for the patients initially treated with ruxolitinib. Subjects initially treated in the anagrelide arm will follow a specific crossover study schedule (see Table 5 and Table 6). Subjects not willing or eligible to continue in the open-label treatment period will be withdrawn from the study.

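### After crossover to ruxolitinib, the Table 6 note makes every scheduled urine pregnancy test depend on local regulations, including the one before the first dose

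*Protocol*

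**What the plan says.** Table 4 schedules urine pregnancy tests on Day 1, every 4 weeks from Week 4 to Week 52, and every 12 weeks from Week 56 for subjects who do not cross over. Its note reads "Females of childbearing potential. Test should be repeated if required by local regulations", and it exempts women with raised FSH or more than a year of amenorrhea. For subjects who cross over, Table 4 refers to Table 6.

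Table 6 marks the urine test at the crossover eligibility visit (Day -1), every 4 weeks to Week 52 after crossover, and every 12 weeks from Week 56. Its note begins "Females of childbearing potential if required by local regulations" and then repeats Table 4's sentence about repeat tests.

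Other relevant text in the Protocol:

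- Section 7.5.6.1 requires a serum test outright at screening and EOT. For urine tests it points to Tables 4 and 6, and adds medical indication and country requirements as further triggers.
- Table 7 asks for a urine test at visits where one is requested.
- Inclusion criterion 8b (Section 3.1) calls for a "negative urinary test before the first dose on Day 1".
- Section 6.3.1 ties entry to the open-label period to the Section 3 criteria. Of a postponed start it says "A delay of up to 4 weeks is permitted for this purpose".
- Section 4.4 names the exclusion criteria as its example of the safety conditions for crossover.
- Table 5 schedules a review of inclusion and exclusion criteria at the eligibility visit: "To determine eligibility for crossover". It repeats the ECOG condition ("Must be 0, 1, or 2 to start ruxolitinib") and notes that "Open-label ruxolitinib may be dispensed at the crossover eligibility visit".

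**The concern.** The clause that governs only repeats in Table 4 governs the scheduled test itself in Table 6. A Group B woman is exposed to ruxolitinib for the first time at crossover, yet her testing rule is weaker than that for a woman continuing ruxolitinib from Group A or staying on anagrelide in Group B. The Protocol gives no reason for this difference.

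Several safety rules depend on detecting a pregnancy. Section 5.5.1 requires withdrawal from treatment after a positive urine test confirmed by serum, and Section 8.5 requires the drug to be stopped at once. Section 1.2.1 reports that ruxolitinib was not teratogenic in rats or rabbits, but that there was minimal embryo-fetal toxicity at the highest doses and more postimplantation loss at higher doses. If the note is followed as written, a site could treat a woman from crossover to EOT with no scheduled pregnancy test that the Protocol firmly requires.

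**Working it through.** Here a test counts as firm if it does not depend on local regulations. Table 4's FSH/amenorrhea exemption still applies to the firm tests it lists.

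**Which text governs after crossover?**

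| Source | Effect on the scheduled urine test |
|---|---|
| Table 4 | Firm; local rules affect repeats only; sends crossover subjects to Table 6 |
| Table 6 | Depends on local rules at all three marked columns |
| Section 7.5.6.1 | Refers back to Tables 4 and 6; only the screening and EOT serum tests are required outright |
| Table 7 | Test when requested; the word is not defined |

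Nothing here restores a firm test under Table 6. The Synopsis plans about 85 sites in the United States and names no other country. Neither document names a local regulation that requires the test.

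**Is a negative test needed before the first ruxolitinib dose?** Section 6.3.1 and the Table 5 criteria review suggest that criterion 8b applies again. Against that, 8b is worded for Day 1, Section 4.4 mentions only exclusion criteria, and Table 5 restates ECOG as a starting condition but not the pregnancy test. The requirement is ambiguous rather than absent.

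**Visit counts, crossover at Week 56**

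- Followed to Week 156 (Section 4.5): 156 − 56 = 100 weeks after crossover.
  - 4-weekly, Weeks 4 to 52: 52/4 = 13.
  - 12-weekly, Weeks 56, 68, 80, 92: 4. If the 12-weekly visits are counted from Week 52 instead (64, 76, 88, 100), the number is still 4.
  - Total 13 + 4 = 17 after the eligibility visit; firm: 0.
- Followed to Week 104 (24 months): 48 weeks after crossover, 48/4 = 12 tests; firm: 0.

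**Same period without crossover (Table 4)**

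- Weeks 68, 80, 92, 104, 116, 128, 140, 152: 8 firm tests to Week 156.
- Weeks 68, 80, 92, 104: 4 firm tests to Week 104.

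**Gap from the last firm test to the first ruxolitinib dose**

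- The last firm test is at Week 52. Crossover at Week 56: 4 × 7 = 28 days. Visit windows of 3 and 7 days add 10, giving 38.
- If the 4-week delay in Section 6.3.1 is added to the transition: 28 + 28 = 56 days, or 66 with windows. If the delay runs from Week 52, the gap stays at 28 (38 with windows).
- Later crossover from open-label anagrelide (allowed by Section 4.1.1): 0 to 12 × 7 = 84 days nominally.

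**Gap to the next firm test.** If EOT is at Week 156, the first firm test after Week 52 is the EOT serum test, 156 − 52 = 104 weeks later.

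**The case against.** The strongest reply is that this is an editorial slip and that the rest of the Protocol favors testing. Table 6 marks the tests. Section 7.5.6.1 treats Tables 4 and 6 alike and lists country requirements as a separate trigger, which would be redundant if Table 6 already meant testing only where local rules demand it. Section 6.3.1 invokes Section 3, which contains 8b, and pregnancy is itself exclusion criterion 15. Table 7 cannot be held against Table 6 alone, because it applies equally to Table 4. The longer gaps rest on adding the delay to the transition, whereas Section 6.3.1 can be read as running the delay from Week 52. The Protocol also refers to country-specific rules in several places, so the Synopsis sentence about sites does not settle which regulations apply.

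Most of this stands. The tests were probably intended, many sites would follow the marks, and the 28-day gap may be the more natural reading. Table 7 adds nothing on either side. There are real safeguards: testing through Week 52, contraception through safety follow-up, the pregnancy exclusion, medically indicated tests, mandatory withdrawal and the EOT serum test.

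None of this changes what the note says. Sites work from the schedule, and the section that would have to override the note refers back to it. What was probably intended is not yet a requirement.

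**Conclusion.** The concern holds. As written, Table 6 leaves 0 of 17 scheduled urine tests firmly required after a Week 56 crossover followed to Week 156 (0 of 12 if followed to Week 104), against 8 (or 4) for a woman who does not cross over. The test at the eligibility visit carries the same condition, so the requirement before the first dose is unclear.

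These counts assume the literal reading of the note and follow-up ending between Weeks 104 and 156; longer follow-up adds one conditional test every 12 weeks. How many tests would actually be missed cannot be determined, because the documents neither state what local regulations require nor give the number of women of childbearing potential who would cross over. Section 1.1 puts median age at diagnosis at about 50 to 60 years, with up to 20% of patients under 40, so the number is probably small but cannot be assumed to be zero. This is a patient-safety wording point that should be corrected. It does not affect sample size, type I error or any efficacy analysis.

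**What to change.** Delete the local-regulation condition from the first sentence of the Table 6 note so that it matches Table 4: "Females of childbearing potential. Test should be repeated if required by local regulations". Carry over Table 4's FSH/amenorrhea exemption if it is meant to apply. Add one sentence: a negative urine test at the crossover eligibility visit is required before the first dose of open-label ruxolitinib.

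The cost is one clause deleted and one sentence added. Where local rules do not already require the tests, up to 1 + 17 = 18 urine tests become mandatory for each woman of childbearing potential who crosses over at Week 56 and is followed to Week 156. All are already marked in Table 6, at visits where hematology and urinalysis are also scheduled, so no visit or assay is added. If lighter testing after crossover was intended, the Protocol should say so and give the reason.
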